#### Reference Methods:

o PEF: Vitalograph spirometer

o FEV₁: Vitalograph spirometer

o RR: Manual count o HR. Pulse Oximeter

## 14.3 Outline Analysis Plan: Statistical Tests and Rationale

#### 14.3.1 Bland-Altman Analysis (Agreement Testing):

Bland Altman is the required standard test to evaluate agreement between devices estimating the same clinical parameter. To do this successfully we require a large enough sample (n large enough) to estimate the mean bias and limits of agreement (LOA) reliably and ensure stable estimates of variability of differences (standard deviation, SD). Bland Altman recommends at least 100 paired observations to estimate CI width around bias and LOA.

> o To assess the mean difference (bias) and Limits of Agreement (LOA) between the new device and the reference.

 Rationale: Identifies systematic bias and variability across measurement ranges.

## 14.3.2 Proportion Within Acceptable Limits:

- Calculation of % of measurements within a pre-defined acceptable range (e.g., ±20% for PEF).
- Rationale: Provides an intuitive clinical interpretation of device performance.

The level of agreement is calculated by showing the percentage of measurements taken by the two approaches that lie within specific limits as a performance measure. For example, using table 14.3.5 which is based on current available target performance data for purpleDx, performance can be used to describe how this agreement can be estimated.

For PEF it is hypothesised that  $\geq 80\%$  of values taken by the two approaches in the same subject will lie within  $\pm 20\%$  of each other. We will calculate for each set of paired data whether the two values are within 20% of each other, and then the proportion of subjects where there is success by this criterion will be calculated. A two-sided confidence level will be calculated around this proportion using the Wilson Score method. The study objective is to demonstrate that the proportion is  $\geq 80\%$  so the study will be positive for this outcome if the lower bound confidence interval is  $\geq 80\%$ .

This figure will be used to determine the number of subjects that we will need to estimate this measure to this level (see section 14.4.2 below).

In a similar way we will use table 14.3.5 (our current estimate of performance) to say we expect to be able to demonstrate what percentage of readings for FEV1, HR and RR from purpleDx (our secondary endpoints) will lie within ± an acceptable percentage of the conventional spirometry, or HR or RR standard device readings. We will calculate for each subject's paired readings, whether the two values lie within this percentage of each other and then the proportion of subjects where this is successful by this criterion for each measure will be calculated. A two-sided confidence interval will be calculated around this proportion using the Wilson Score method based on the subject numbers determined above. Subsequent sensitivity testing will allow upgraded description of device performance (see section 14.4.4).

#### Formula for deciding whether paired values are within a percentage range.

There are two approaches to this calculation, namely relative percent difference or the symmetric formula. The latter avoids bias, when either value could be the reference, but for this study we have our fixed 'gold' standard and hence we have chosen to use the relative percent difference.

Using: Pi = test device reading for subject i

Gi = gold standard reading for subject i

Success =  $Pi - Gi \le 0.2 \times Gi$ 

This approach measures deviation relative to the gold standard as in this study.

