## 14.4 Sample Size Calculation

## **14.4.1 PEF Sample Size Calculation** (to show lower 95% CI bound ≥80%)

Study goal:

- True success proportion p1
- Null threshold (target to exceed) p0=0.80
- Type I error (2-sided): α=0.05
- Power:  $1-\beta=0.90$
- Use **Wilson score CI** to test whether lower bound ≥ 0.80.

Approximate approach (one-sample proportion power analysis)

We can approximate using a **one-sample proportion test** (binomial test of  $H_0$ : p = 0.80 vs  $H_1$ :  $p = p_1 > 0.80$ ):

$$n = rac{\left[z_{1-lpha/2}\sqrt{p_0(1-p_0)} + z_{1-eta}\sqrt{p_1(1-p_1)}
ight]^2}{(p_1-p_0)^2}$$

This gives the approximate number of *paired comparisons* (subjects) needed.

Where:

- $z1-\alpha/2=1.96$  for  $\alpha=0.05$
- $z1-\beta=1.2816$  for 90% power

Example calculation

Expected true agreement proportion p1=0.90.

Then:

$$p_0 = 0.80, \quad p_1 = 0.90 \ n = rac{(1.96\sqrt{0.8 imes 0.2} + 1.2816\sqrt{0.9 imes 0.1})^2}{(0.9 - 0.8)^2}$$

Computing:

$$\sqrt{0.8 \times 0.2} = 0.4, \quad \sqrt{0.9 \times 0.1} = 0.3$$

$$n = \frac{(1.96(0.4) + 1.2816(0.3))^2}{(0.1)^2} = \frac{(0.784 + 0.384)^2}{0.01} = \frac{1.168^2}{0.01} = \frac{1.364}{0.01} = 136.4$$

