# 14.10 Estimand Table

Component	PEF	FEV 1	RR	HR
Treatment	Measurement using new device	Measurement using new device	Measurement using new device	Measurement using new device
Comparator	Vitalograph spirometer	Vitalograph spirometer	Manual count	Pulse oximeter
Population	Adults ≥18 years presenting to ED with respiratory / cardiorespiratory symptoms	Same as PEF	Same as PEF	Same as PEF
Variable (Endpoint)	Peak Expiratory Flow; PEF (L/min)	Forced Expiratory Volume in One Second; FEV 1 (L)	Respiratory Rate; RR (Breaths per minute)	Heart Rate; HR (beats per minute)
Summary Measure	Mean bias, 95% Limits of Agreement, % within ± 20% of reference	Mean bias, 95% Limits of Agreement, % within ±10%	Mean bias, 95% Limits of Agreement, % within ±10%	Mean bias, 95% Limits of Agreement, % within ±10%
Handling of Missing Data	Exclude invalid readings; perform sensitivity analysis if needed	Same as PEF	Same as PEF	Same as PEF
Intercurrent Events	Poor technique, device malfunction	Spirometry effort failure, device errors	Talking during measurement, movement artefact	Movement artefact, device connectivity issues
Interpretation	Agreement sufficient for clinical decision support at bedside	Agreement comparable to spirometry for diagnosis and monitoring	Agreement sufficient for respiratory distress assessment and monitoring	Agreement sufficient for accurate triage and monitoring

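### The PEF success formula in 14.3.2, as supplied, has no absolute value and so contradicts the two-sided ±20% criterion; coded literally, it scores every under-reading as a success.

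*Protocol*

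**What the plan says.** In words, the PEF criterion is two-sided wherever it appears in the protocol.

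- Section 14.3.2: "We will calculate for each set of paired data whether the two values are within 20% of each other".
- Section 14.3.5 (repeated in 7.4 and 14.9): at least 80% within ±20%, with a bias target of ±10%.
- Section 14.10, PEF summary measure: the percentage "within ± 20% of reference".

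The decision rule in 14.3.2 is that "the study will be positive for this outcome if the lower bound confidence interval is" at least 80%, using the Wilson score interval. Section 14.4.1 sizes the study on the same benchmark: "Null threshold (target to exceed) p0=0.80", "Expected true agreement proportion p1=0.90" and "Type I error (2-sided): α=0.05".

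The only operational definition of a subject's success is in the unnumbered formula block that closes 14.3.2. It considers a symmetric formula, chooses the relative difference because the study has a fixed reference, and gives, in the text as supplied:

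Success = Pi - Gi ≤ 0.2 × Gi

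The sentence after it reads "This approach measures deviation relative to the gold standard as in this study". Neither an absolute value nor a lower limit appears.

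**The concern.** The formula and the criterion describe different events. With a spirometer value of 500 L/min, ±20% means 400 to 600 L/min. A purpleDx reading of 250 L/min gives 250 - 500 = -250, which is below 0.2 × 500 = 100, so the formula calls it a success. Only over-reading by more than 20% can fail.

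This line defines the numerator of the primary proportion, and it is the line that a programmer would most naturally code. The rule for a positive PEF outcome rests on the Wilson bound alone; the ±10% bias target in 14.3.5 is not a condition of it. Section 14.3.2 also carries the proportion method over to FEV1, RR and HR, so a literal reading could spread to the secondary endpoints. If that happened, p0 = 0.80 would be compared with a quantity it was not set for.

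**Working it through.** **Inputs.** From 14.4.1: p0 = 0.80, p1 = 0.90, two-sided alpha 0.05 (z = 1.96), power 0.90 (z = 1.2816), 137 pairs. The same section aims for 150 analysable data sets and caps recruitment at 160. From 14.3.5: tolerance ±20%, bias target ±10%. The protocol gives no distribution of the differences and no split of misses above and below the reference, so these are assumed below.

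**1. The plan's own figure.** n = (1.96 × 0.4 + 1.2816 × 0.3)² / 0.1² = (0.784 + 0.38448)² / 0.01 = 136.5, so 137. The protocol's 136.4 differs only by rounding.

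**2. The pass mark.** The Wilson lower bound is

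[p + z²/(2n) - z√(p(1-p)/n + z²/(4n²))] / (1 + z²/n), with p = x/n.

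At n = 137 it first reaches 0.80 at x = 119 (0.8019; 118 gives 0.7935). At n = 150 this happens at x = 130 (0.8030; 129 gives 0.7954).

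**3. Behaviour with the two-sided criterion (exact binomial).** At n = 137, P(X ≥ 119) is 2.4% if the true proportion is 0.80 and 91.0% if it is 0.90. At n = 150 the figures are 2.2% and 92.8%. The design works as intended.

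**4. Behaviour with the formula read literally.** Let D = 100 × (Pi - Gi)/Gi be normal with mean b and SD s. Choose s so that exactly 80% lie within ±20%:

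Φ((20 - b)/s) - Φ((-20 - b)/s) = 0.80.

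The literal formula scores q = Φ((20 - b)/s). For b = 0, s = 15.61 and q = Φ(20/15.61) = Φ(1.28) = 0.90. The chance of passing is then P(X ≥ 119) at n = 137, or P(X ≥ 130) at n = 150, with success probability q.

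| Bias b | SD s | Truly within ±20% | Scored as success, q | Pass, n = 137 | Pass, n = 150 |
|---|---|---|---|---|---|
| -10% | 11.63 | 0.80 | 0.995 | about 100% | about 100% |
| -5% | 14.76 | 0.80 | 0.955 | about 100% | about 100% |
| 0 | 15.61 | 0.80 | 0.900 | 91% | 93% |
| +5% | 14.76 | 0.80 | 0.845 | 27% | 28% |
| +10% | 11.63 | 0.80 | 0.805 | 3.4% | 3.1% |

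If all misses were above the reference, q would be 0.80 and the pass rate 2.4% at n = 137. If the ratio Pi/Gi is lognormal and unbiased on the log scale, again with 80% within ±20%, q = 0.877 and the pass rate at n = 137 is 68%.

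The 91% equals the power in step 3 for a simple reason. With no bias, the 10% of readings that miss low are re-scored as successes, which lifts 0.80 to 0.90, the design alternative.

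**The case against.** **The bars may be an artefact.** The text was read from a PDF by a program, and inline subscripts in this section are already flattened (Pi, Gi). Thin vertical bars could have been lost in the same way. This stands: the supplied text cannot show that the signed protocol prints a one-sided rule.

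**The intention is clear.** Every verbal statement of the criterion is two-sided, and so are the tolerance bands in 14.6. This also stands, and it makes a notation error the likely explanation. It does not remove the need for a correction if the bars are absent, because the formula is the only place where a success is defined for computation.

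**Gross under-reading would be seen.** The Bland-Altman bias and limits of agreement are part of the PEF summary measure in 14.10. That is right, so a reader should not infer that under-reading would go unnoticed in the report. The Bland-Altman results are not, however, a condition of the positive-outcome rule.

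**Relative or symmetric difference.** The phrase in 14.3.2 about the two values being close to each other sounds symmetric. The formula block chooses the relative difference and gives its reason, and 14.10 confirms the reference as denominator. That question is settled; rewording the phrase is tidying only.

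**Conclusion.** The formula as supplied contradicts the criterion it is meant to implement, and the two must be reconciled before the data are analysed. It is probably a slip of notation, and the consequence follows only if the line is programmed literally.

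In that case, for a device with exactly 80% of readings truly within ±20% and normal relative differences, the chance of passing at n = 137 would be 91% with no bias, against the intended 2.4%. Across the protocol's own ±10% bias target it would run from about 3% (bias +10%) to about 100% (bias -5% or -10%).

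A reader might infer that any device at the 80% benchmark passes about 91% of the time. The documents do not support that: the figure needs zero bias and misses split equally above and below, and the protocol gives no data on either. Nor do they support a claim that purpleDx is prone to under-read PEF, or that the planned test has lost its error control. With the two-sided criterion its false-pass rate is 2.4%, and the 137 subjects reproduce.

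**What to change.** Check the formula in the source document first. If the absolute-value bars are there, no change to the formula is needed.

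If they are absent, state in 14.3.2:

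Success = |Pi - Gi| ≤ 0.2 × Gi, that is, 0.8 × Gi ≤ Pi ≤ 1.2 × Gi.

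Use the same form for FEV1, RR and HR, with each parameter's own tolerance in place of 0.2.

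Optionally, reword the sentence in 14.3.2 that compares the two values with each other so that it refers to ±20% of the reference value, in line with the formula block and 14.10.

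The cost is a line or two of protocol wording. No further data are needed, and the sample size of 137 stays as it is, with exact power of 91% at a true proportion of 0.90.

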# 14.3.3 Intraclass Correlation Coefficient (ICC):

- Used to assess reliability/agreement between two quantitative measurements.
- Rationale: ICC >0.75 indicates good agreement, ICC >0.90 indicates excellent agreement.
- o Provides an important link with established literature for comparison.

# 14.3.4 Descriptive Statistics (Usability):

- Mean and SD for Likert-scale usability ratings.
- o Error rates, setup time, and qualitative feedback summarised.

## 14.3.5 Parameter Hypothesis Table: Acceptable Agreement Thresholds

Parameter	Performance Range	Likely Performance of Device  (% Within Limits of Reference Values)	Bias Target	Expected Acceptable Level Of Agreement
PEF	350 – 700 L/min	≥ 80% within ± 20%	± 10%	± 20%
FEV 1	2-5L	≥ 95% within ± 10%	± 0.1 L	± 0.2 – 0.25 L
RR	6 – 20 breaths per minute (Bpm)	≥ 95% within ± 10%	± 2 Bpm	± 4 Bpm
HR	50 – 120 beats per minute	≥ 95% within ± 10%	± 5 bpm	± 1 bpm

(bpm)		

## 14.4 Sample Size Calculation

## **14.4.1 PEF Sample Size Calculation** (to show lower 95% CI bound ≥80%)

Study goal:

- True success proportion p1
- Null threshold (target to exceed) p0=0.80
- Type I error (2-sided): α=0.05
- Power:  $1-\beta=0.90$
- Use **Wilson score CI** to test whether lower bound ≥ 0.80.

Approximate approach (one-sample proportion power analysis)

We can approximate using a **one-sample proportion test** (binomial test of  $H_0$ : p = 0.80 vs  $H_1$ :  $p = p_1 > 0.80$ ):

$$n = rac{\left[z_{1-lpha/2}\sqrt{p_0(1-p_0)} + z_{1-eta}\sqrt{p_1(1-p_1)}
ight]^2}{(p_1-p_0)^2}$$

This gives the approximate number of *paired comparisons* (subjects) needed.

Where:

- $z1-\alpha/2=1.96$  for  $\alpha=0.05$
- $z1-\beta=1.2816$  for 90% power

Example calculation

Expected true agreement proportion p1=0.90.

Then:

$$p_0 = 0.80, \quad p_1 = 0.90 \ n = rac{(1.96\sqrt{0.8 imes 0.2} + 1.2816\sqrt{0.9 imes 0.1})^2}{(0.9 - 0.8)^2}$$

Computing:

$$\sqrt{0.8 \times 0.2} = 0.4, \quad \sqrt{0.9 \times 0.1} = 0.3$$

$$n = \frac{(1.96(0.4) + 1.2816(0.3))^2}{(0.1)^2} = \frac{(0.784 + 0.384)^2}{0.01} = \frac{1.168^2}{0.01} = \frac{1.364}{0.01} = 136.4$$

#### This means:

With 137 paired results (one per subject), if the *true* success rate is 90%, there is 90% power that the 95% lower Wilson bound will exceed 80%.

To ensure sample size of 137 can be achieved, the maximum number of patients recruited into the study will be 160. This allows for withdrawals or failures to capture measurements for any reason.

Once 150 patients have been recruited, the preliminary data will be reviewed to determine whether any further patients are required for the study or whether sufficient data has been collected to enable the statistics to be performed. Recruitment will cease once sufficient data has been shown to have been collected from at least 150 patients. A maximum of 160 patients will be recruited to achieve 150 analysable sets of data.

## 14.4.2 FEV1 Sample Size Calculation

From Table 14.3.5 we might expect the performance of the purpleDx device to be closer to  $\leq$  10% of the gold standard. However, across a broader range of clinical subjects as in this case, we are uncertain of the performance and to allow us to define the performance we will use the same threshold settings as for PEF.

However, we can calculate a table of performance of the device for p0 and power for n=150, p1=0.95 and  $\alpha$ =0.05 above using a rearrangement of the formula:

$$z_{1-eta} = rac{(p_1-p_0)\sqrt{n} - z_{1-lpha/2}\sqrt{p_0(1-p_0)}}{\sqrt{p_1(1-p_1)}}$$

Target p0	Power
0.85	99%
0.88	84%
0.89	71%
0.90	54%

Thus with 150 subjects and a true agreement of 95% we can demonstrate that the lower CI exceeds 0.88 with about 80-85% power sufficient for this study.

## 14.4.3 HR and RR Sample Size Calculation

150 subjects (calculation as above for FEV1)

Our aim as above is to define the percentage agreement as so that a positive result is achieved >or=80% if the CI lower bound is >or= 80%. Again, we would expect the agreement to be better than this but will need this number of subjects to ensure the precision of this proportion-of-agreement around the calculated CI margin. This ensures we can reliably quote the performance of the purpleDx device across these measures.

## 14.4.4 Sample Size for Intraclass Correlation

- FEV1 (vs Vitalograph spirometry)
- HR (vs pulse oximeter)
- RR (vs manual count)

Our sample size needs to allow us to evaluate a Null Hypothesis: an ICC of less than or equal to 0.75 (moderate agreement) vs an Alternative Hypothesis: ICC equal to or better than 0.90 with a power of 0.80 and alpha of 0.05.

Using Bonnett's formula (2002)

$$n = \left[rac{Z_{1-lpha/2} + Z_{1-eta}}{\ln\left(rac{1+
ho_a}{1-
ho_a}
ight) - \ln\left(rac{1+
ho_0}{1-
ho_0}
ight)}
ight]^2 + 1.$$

n ≈ 47-50 is needed to detect an ICC ≥ 0.90 versus null ICC of 0.75

**n > 100** provides excellent power for secondary ICC analyses, especially if some readings are invalid.

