## Sensitivity Analyses:

- Sensitivity analyses will be considered if >10% of data for any parameter are missing.
  - For PEF, imputation methods such as last observation carried forward (LOCF) or single imputation using median of available efforts may be considered for exploratory purposes
  - For usability outcomes, missing questionnaire responses will not be imputed; proportions will be based on available data.

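### Section 14.4.4's ICC sample size of 47-50 does not follow from its printed formula (which gives 9 and lacks a factor of 4), and section 14.4.1 ties one cap of 160 to two analysable targets, 137 and 150, with no stated loss rate

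*Protocol*

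**What the plan says.** **ICC size (Protocol 14.4.4).** The null is an ICC of at most 0.75 and the alternative is "ICC equal to or better than 0.90 with a power of 0.80 and alpha of 0.05". The section prints a formula on the difference of two log terms, ln((1+ρ)/(1−ρ)) at 0.90 and at 0.75, using the two-sided normal quantile. It concludes that "n ≈ 47-50 is needed to detect an ICC ≥ 0.90 versus null ICC of 0.75". It then adds that more than 100 subjects give excellent power for the secondary ICC analyses.

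**Recruitment cap (Protocol 14.4.1).** The PEF calculation needs 137 pairs. The text then gives two purposes for the same cap. First: "To ensure sample size of 137 can be achieved, the maximum number of patients recruited into the study will be 160", which is said to allow for withdrawals and failed measurements. Then: "A maximum of 160 patients will be recruited to achieve 150 analysable sets of data". Once 150 have been recruited, "the preliminary data will be reviewed to determine whether any further patients are required" or whether there is already enough to run the statistics.

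**Secondary endpoints (Protocol 14.4.2 and 14.4.3).** The FEV1 power table uses n = 150, a true agreement of 95% and several lower bounds. It concludes that power is about 80-85% against 0.88. HR and RR take the same 150.

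**Missing data (Protocol 14.7.3).** Analyses use complete cases for each parameter. "Sensitivity analyses will be considered if >10% of data for any parameter are missing". No expected loss rate is given anywhere.

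**The concern.** Section 14.4.4 prints the formula, every input and the result, so a reader can check it, and the result does not come out. The figures differ about fivefold, which is too much for rounding. The formula itself also gives too small a size for a comparison of two measurements per subject. Anyone who reused it as printed would plan a badly underpowered ICC test.

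In section 14.4.1 one number, 160, serves two targets that imply different tolerances for loss. If 137 is the target, more than twice as much loss is tolerable as when 150 is. The secondary power figures assume the larger target, so how firmly they stand depends on a loss rate that the document does not state.

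**Working it through.** **Part 1: ICC size**

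Inputs, all from section 14.4.4: ρ0 = 0.75, ρa = 0.90, two-sided alpha 0.05 (z = 1.960), power 0.80 (z = 0.8416).

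*Printed formula.*
- ln(1.90/0.10) − ln(1.75/0.25) = ln 19 − ln 7 = 0.9985
- (1.960 + 0.8416)² / 0.9985² = 7.849 / 0.9971 = 7.872
- n = 7.872 + 1 = 8.87, so **9**, against the stated 47-50

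*Corrected formula.* With two measurements per subject the usual transform is ½·ln((1+ρ)/(1−ρ)). The ½ halves the difference in the denominator, so it multiplies the leading term by 4:
- n = 4 × 7.872 + 1 = 32.49, so **33**

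*Can another reading rescue 47-50?* At alpha 0.05 and power 0.80, the variants tried (one-sided, with and without the ½, +3 in place of +1, three measurements) run from 8 to 35. Only changed inputs come near. With the ½, power 0.90 and +3 the result is 46. With the ½ and two-sided alpha 0.01 it is 48-50. Neither matches the stated inputs.

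*Power of the exact F test, two measurements, one-sided 0.025:*

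| n | Power |
|---|---|
| 9 | 27.5% |
| 33 | 80.1% |
| 47 to 50 | 92% to 94% |
| 100 | over 99.8% |
| 137 to 150 | over 99.9% |

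**Part 2: the cap of 160**

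*Figures in section 14.4 that reproduce.* The PEF formula gives (0.784 + 0.384)²/0.01, which is 136.5, so 137. The FEV1 table recomputes as 99.2%, 84.4%, 71.2% and 54.5%, against the stated 99, 84, 71 and 54%.

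*Loss room implied by each target.*
- 137 of 160: 1 − 137/160 = 23/160 = 14.4%
- 150 of 160: 1 − 150/160 = 10/160 = 6.25%

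*Yield from 160 recruits.* The protocol gives no loss rate, so every rate below is an assumption. Losses are taken as independent with a common rate.

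| Assumed loss | Expected sets | P(at least 150) | P(at least 137) | Recruits for 150 expected |
|---|---|---|---|---|
| 5% | 152 | 82% | over 99.9% | 158 |
| 6.25% | 150 | 58% | over 99.9% | 160 |
| 8% | 147 | 26% | 99.8% | 164 |
| 10% | 144 | 6.7% | 97% | 167 |
| 14.4% | 137 | 0.1% | 56% | 176 |

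*FEV1 power against 0.88, true agreement 0.95.* The formula column uses the rearranged formula of section 14.4.2. The exact column is the binomial probability that the Wilson lower bound reaches 0.88.

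| Pairs | Protocol formula | Exact |
|---|---|---|
| 137 | 79.9% | 75.2% |
| 144 | 82.4% | 81.5% |
| 150 | 84.4% | 86.8% |

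**The case against.** **The ICC error has no consequence.** The stated 47-50 exceeds both 9 and 33, the ICC is a secondary analysis, and recruitment is driven by 137 and 150. This stands in full. What remains is a printed formula and a printed result that contradict each other.

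**The plan does not forecast a loss that defeats 150.** A reader might take the 10% in section 14.7.3 as expected missingness and conclude that 160 recruits cannot deliver 150 sets. The document does not support that. The 10% is only a trigger for considering sensitivity analyses, and no rate is forecast. Several features limit loss: a single visit, up to three retry scans (Appendix 3), and acceptance of one valid effort for PEF and FEV1 (14.7.2). At an assumed 2% loss the chance of at least 150 is above 99.9%. This objection stands. Only the double target and the absent rate survive it.

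**The secondary power is hardly threatened.** The 0.88 bound is illustrative. Sections 14.4.2 and 14.4.3 carry over the PEF threshold of 0.80, and with 137 pairs and a true 95% the power against 0.80 is above 99.9%. Even against 0.88, 144 pairs stay within the stated 80-85%. Setting the exact 75.2% at 137 beside the formula's 84% at 150 would exaggerate the drop, because the two figures use different methods. The like-for-like pairs are 79.9% against 84.4% and 75.2% against 86.8%.

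**The review at 150 is not shown to inflate type I error.** The words "the preliminary data will be reviewed to determine whether any further patients are required" could be read as a look at agreement results. Their context concerns whether enough data have been collected to run the statistics, which reads as a completeness count. The protocol contains no rule to extend recruitment when the bound is missed, so any inflation figure would rest on an invented rule. The exact one-sided error also differs between fixed sizes with no look at all: 2.24% at 150 and 2.64% at 160.

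**Conclusion.** Two corrections hold, and neither changes how many patients are needed.

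1. The ICC size in section 14.4.4 is wrong as written. The printed formula gives 9, the form for two measurements gives 33, and no variant tried at the stated alpha and power gives 47-50. This rests only on the section's own inputs and on a comparison of two measurements per subject. The error is on the safe side.

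2. Section 14.4.1 justifies one cap by two analysable targets, with implied loss room of 14.4% and 6.25% and no stated rate. Whether 150 is reached depends wholly on that rate: 82% probability at an assumed 5% loss, 6.7% at an assumed 10%. The primary analysis is well protected, with 97% probability of 137 pairs at 10% loss. For FEV1 against the illustrative 0.88 bound, falling from 150 to 137 pairs costs about 4.5 percentage points by the protocol's formula (84.4 − 79.9) and about 11.6 on the exact calculation (86.8 − 75.2).

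**What to change.** - **Section 14.4.4:** put the factor 1/2 on both log terms, or equivalently multiply the leading term by 4. Restate n = 33 for 80% power, with power over 99.8% at 100 or more. If 47-50 was meant for a different power or alpha, state those inputs instead.
- **Section 14.4.1:** name one analysable target and the loss rate assumed in setting 160. If the target is 137, the existing cap allows up to 14.4% loss. If it is 150, say why loss is expected to be at most 6.25%.
- **Sections 14.4.2 and 14.4.3:** give power at 137 beside 150, using one method throughout. For FEV1 against 0.88 that is 79.9% and 84.4% by the protocol's formula, or 75.2% and 86.8% exact.
- **Optional clarification:** add a sentence saying that the check at 150 recruits counts valid pairs only.

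The cost is a few restated figures and two or three sentences, with no extra patients. The stated secondary power becomes slightly less favourable at the lower target.
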